#### **14.6 Communication and Publication of Results**

Where required by applicable regulatory requirements, an Investigator signatory will be identified for the approval of the CSR. The Investigator will be provided appropriate access to statistical tables, figures, and relevant reports and will have the opportunity to review the complete study results at NeRRe or another mutually agreeable location.

The original eCRFs and all data generated during the study under this protocol will become the property of the Sponsor.

Upon completion of the CSR, NeRRe will ensure public disclosure of the clinical trial research results according to the NeRRe's SOP and provide each Investigator with the full summary of the study results. The Investigator is encouraged to share the summary results with the study subjects, as appropriate.

It is the intent of all parties that the results of the study be published in a timely manner consistent with academic standards and with due consideration given to the protection of intellectual property rights. The Principal Investigator and NeRRe will be responsible for writing the proposed publication; this must happen with due diligence and with minimal delay.

Any proposed publication or presentation (including a manuscript, abstract or poster) originated by an Investigator for submission to a journal or scientific meeting should be sent to the Sponsor for review at least sixty days prior to submission. The Sponsor's comments on the proposed publication shall be considered in good faith by the authors. Sponsor may delay such submission by a maximum of six months if it reasonably believes that publication of results may compromise its intellectual property rights or else insist that such information or data is removed from the proposed publication. Publication of the results will not include confidential information without the permission of the Sponsor.

#### **14.7 Indemnification**

In the event of study-related damage or injuries, the clinical trial insurance of the Sponsor provides compensation for claims that arise in accordance with the regulatory requirements of the countries involved, except for claims that arise from willful misconduct or gross negligence. A copy of the country-specific insurance certificates will be held in the TMF and in the Investigator Site File.

---

**17. APPENDICES****APPENDIX A: LIST OF PROHIBITED CONCOMITANT MEDICATIONS**

The following is a comprehensive (but not exhaustive list\*) of prohibited concomitant medications.

\* *Recently approved drugs may not be included in the list and should be checked on a case-by-case basis.*

Prohibited from the time shown until 1 week after the last dose of study medication	
Medications potentially confounding efficacy	
Hormonal therapies
 
 
• Vaginal hormonal products (rings, creams, gels and including DHEA or analogues thereof) – from 1 week prior to Screening Visit 2
 
• Transdermal oestrogen alone or or oestrogen/progestin products - from 4 weeks prior to Screening Visit 2
 
• Oral oestrogen (including selective oestrogen receptor modulators) and/or progestin therapy - – from 8 weeks prior to Screening Visit 2
 
• Intrauterine progestin therapy – from 8 weeks prior to Screening Visit 2
 
• Progestin implants and oestrogen alone injectable drug therapy – from 3 months prior to Screening Visit 2
 
• Oestrogen pellet therapy or progestin injectable drug therapy - – from 6 months prior to Screening Visit 2
 
 
Non-hormonal therapies
 
Non-hormonal prescription (eg paroxetine, other anti-depressants including selective serotonin reuptake inhibitors, serotonin norepinephrine reuptake inhibitors and tri-cyclic antidepressants, alpha agonists [clonidine], methyl dopa, gabapentin, pregabalin, medicinal cannabis or derivatives) or over the counter/herbal treatments for treatment of menopausal symptoms is not allowed throughout the study. Subjects must have discontinued these drugs at least 28 days prior to Screening Visit 2. Subjects may, however, be permitted to continue to use these drugs if the dose has been stable for at least 4 weeks and they have been prescribed solely for the management of another disorder (e.g. neuropathic pain, depression).

Prohibited from Screening Visit 2 until 1 week after the last dose of study medication	
CYP3A4 substrates with a narrow therapeutic range	alfentanil, astemizole, cisapride, cyclosporine, dihydroergotamine, ergotamine, fentanyl, pimozone, quinidine, sirolimus, tacrolimus, terfenadine
Strong or moderate	clarithromycin, atazanavir, idelalisib, nefazodone, nelfinavir,

inhibitors of CYP3A4	boceprevir, cobicistat, danoprevir and ritonavir, elvitegravir and ritonavir, grapefruit juice, indinavir and ritonavir, itraconazole, ketoconazole, lopinavir and ritonavir, paritaprevir and ritonavir and (ombitasvir and/or dasabuvir), posaconazole, ritonavir, saquinavir and ritonavir, telaprevir, tipranavir and ritonavir, troleandomycin, voriconazole  aprepitant, cimetidine, ciprofloxacin, clotrimazole, crizotinib, cyclosporine, dronedarone, fluconazole, fluvoxamine, imatinib, tofisopam, verapamil, troleandomycin, ciprofloxacin
P-glycoprotein inhibitors	azithromycin, conivaptan, cyclosporine, diltiazem, erythromycin, felodipine, ketoconazole, quinidine, ranolazine,  amiodarone, carvedilol, clarithromycin, dronedarone, itraconazole, lapatinib, propafenone, quinidine,
P-glycoprotein substrates with a narrow therapeutic range	Digoxin
Prohibited from Screening Visit 2 until Week 12	
Strong or moderate inducers of CYP3A4	rifampicin, carbamazepine, efavirenz, bosentan, modafinil, St. John's Wort, enzalutamide, mitotane, phenytoin, etravirine

[figure not shown]
**APPENDIX B: PHASE 2B ADAPTIVE DOSE-FINDING DESIGN FOR NT-814  
EFFECT ON REDUCTION OF HOT FLUSHES**[name]  
18 July 2018**INTRODUCTION AND PURPOSE**

A Phase 2b dose-finding placebo-controlled trial of NT-814 treatment with four different doses for 12 weeks aimed at reduction of hot flushes is being planned. Adaptive design options are being considered to modify randomization ratios to the NT-814 doses based on accumulating data. This report summarizes several example adaptive design options along with their performance characteristics for an initial assumed example set of potential TRUE underlying dose-response curves. The primary endpoints for the trial are hot flush frequency and severity; however, the adaptive design simulation software cannot handle multiple endpoints. Hence, the scenarios evaluated focus on reduction of hot flush frequency.

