The PK exposure-response relationship will be established through the correlation of plasma NT-814 concentrations derived from sparse sampling, with appropriate clinical efficacy endpoints. Sparse sampling is a well-established method of collecting PK data that avoids the need for multiple blood draws and extended clinic visits.

The safety of NT-814 will be assessed using standard measures of safety appropriate for the stage of development (adverse events, routine safety laboratory tests, vital signs, electrocardiogram (ECG)). Although the effect is expected to be modest in the post-menopausal population, NK3 receptor blockade may result in a reduction in circulating oestrogen concentrations and so safety assessments will, additionally, include an assessment of bone turnover. No adverse effects are anticipated but because NT-814 acts centrally in the nervous system its safety related to suicidal ideation will, in accordance with regulatory expectations, be assessed using the electronic version of the Columbia Suicide Severity Rating Score.

The assessment of safety for hormonal menopause therapies typically includes evaluation of the endometrium by trans-vaginal ultrasound (TVU) and, if indicated, endometrial biopsy. Since NK receptor blockade will, if anything, reduce hormonal drive to the endometrium these invasive evaluations are not warranted routinely for all subjects. However, any subject experiencing uterine bleeding (including spotting) during the study will undergo TVU and biopsy if indicated.

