### **8.5 Safety endpoints**

- Change from baseline in clinical laboratory assessments
  - At Weeks 2, 4, 12 and 16 for haematology and urinalysis
  - At Weeks 2, 4, 8, 12 and 16 for clinical chemistry
- Change from baseline in vital signs (blood pressure, pulse rate, temperature) at Weeks 2, 4, 8, 12 and 16
- Change from baseline in weight, waist circumference and body mass index at Weeks 2, 4, 8, 12 and 16
- Proportion of subjects with clinically significant abnormal ECG findings at each visit
- Proportion of subjects with non-significant abnormal ECG findings at each visit
- Change from baseline at Weeks 2, 4, 8, 12 and 16 in ECG intervals (RR, PR, QT, QTc and QTcF)
- Proportion of subjects with maximum absolute QTcF values by category at each visit
  - $\leq 450$ ,  $>450$  to  $\leq 480$ ,  $>480$  to  $\leq 500$ ,  $>500$  msec
- Proportion of subjects with maximum change from baseline in ECG QTcF values by category at Weeks 2, 4, 8, 12 and 16
  - $\leq 0$ ,  $>0$  to  $\leq 30$ ,  $>30$  to  $\leq 60$ ,  $>60$  msec
- Change from baseline in the electronic Columbia Suicide Severity Rating Scale (eC-SSRS) at Weeks 4, 12 and 16
- Change from baseline to Weeks 12 and 16 in:
  - Serum concentration of bone-specific alkaline phosphatase (BALP)
  - Serum concentration of procollagen type 1 N-terminal propeptide (P1NP)
- Nature and severity of AEs
- Withdrawals due to an AE
- Use of concomitant medications

[figure not shown]

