#### **8.6.7 Final Follow-up / Early Termination visit**

Subjects will return to the clinic for the final study visit 4-weeks ( $\pm 5$  days) after the end of treatment. The visit should be conducted at a similar time of day to the baseline visit to reduce diurnal variation in the plasma bone turnover markers.

The same procedures will also be undertaken if a subject withdraws from the study early.

The eDiary will be collected and the following assessments completed:

- Symptom directed physical examination
- Vital signs (after resting for  $\geq 5$  mins per Section 10.3.8)
- 12-lead ECG
- Blood samples for clinical chemistry and hematology and plasma bone turnover markers
- Urine sample for urinalysis
- Subjects will be asked to complete the MenQoL, HFRDIS, Pittsburg Sleep Quality Index, Insomnia Severity Index, eC-SSRS and the Beck Depression Inventory II
- Review for adverse events and changes in concomitant medications

Subjects may be re-started on any prohibited medications and menopausal symptom management medications at this time.

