### **9.8 Prohibited Concomitant Medication**

A list of prohibited medications is provided in Appendix A.

The use of hormonal therapies is prohibited prior to Screening Visit 2 for the periods stated in exclusion criterion 1, and throughout out the study.

The use of non-hormonal prescription (eg paroxetine, other anti-depressants, alpha agonists [eg clonidine], methyl dopa, gabapentin, pregabalin, medicinal cannabis) or over the counter/herbal treatments for treatment of menopausal symptoms is not allowed throughout the study. Subjects must have discontinued these drugs at least 28 days prior to Screening Visit 2. Subjects may, however, be permitted to continue to use these drugs if the dose has been stable for at least 4 weeks and they have been prescribed solely for the management of another disorder (e.g. neuropathic pain, depression).

The following medications are also excluded from Screening Visit 2 until the last dose of IMP (unless stated otherwise).

- Known CYP3A4 substrates with a narrow therapeutic range
- Strong or moderate inhibitors of CYP3A4
- Strong or moderate inducers of CYP3A4 (until Week 12 only)
- Known P-glycoprotein inhibitors
- Digoxin

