### **10.3.9 Bone Turnover Markers**

Blood for assessment of bone turnover markers will be collected at Baseline, Week 12 and Week 16 and sent to the central laboratory for analysis. The serum concentration of the following markers will be assessed: bone-specific alkaline phosphatase (BALP) and procollagen type 1 N-terminal pro-peptide (P1NP).

Baseline and Week 12 and 16 visits should be conducted at similar times of day to reduce diurnal variation in these markers.

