### 3. SUBJECT POPULATIONS

#### 3.1. Population Definitions

The following subject populations will be evaluated and used for presentation and analysis of the data:

**Screen Analysis Set:** the screened population will include all subjects with informed consent.

**Randomized Analysis Set:** the randomized population will include all subjects with a randomization date and number.

**Safety Analysis Set:** All subjects who receive at least one dose of double-blind study drug irrespective of treatment received. Subjects will be analysed according to treatment received.

**Full Analysis Set (FAS):** All randomised subjects who received at least one dose of double-blind study drug, irrespective of treatment received, and have hot flush data for at least 7 days' worth of post-treatment assessments (i.e. requirement for the primary efficacy endpoint). Subjects will be analysed according to randomised treatment. This is the primary efficacy analysis set for the study.

**Modified Full Analysis Set (mFAS):** All subjects in the FAS excluding those who took non-hormonal treatments (anti-depressants, alpha-2 agonists, gabapentinoids and cannabis) or over the counter herbal treatments (intended to treat menopausal symptoms) that may have had a confounding effect on hot flash frequency and/or severity at any time during the study (defined as within 28 days before the start of Screening Visit 2 through to the Week 12 visit, inclusive). The medications entered in EDC have been reviewed by Sponsor's blinded Medical Expert, and the following final list of PREFERRED NAME was confirmed:

CLONIDINE  
CLONIDINE HYDROCHLORIDE  
CIMICIFUGA RACEMOSA  
TRIFOLIUM PRATENSE  
CIMICIFUGA RACEMOSA;HYPERICUM PERFORATUM  
CANNABIS SATIVA  
GABAPENTIN  
PREGABALIN  
AMITRIPTYLINE  
NORTRIPTYLINE  
CITALOPRAM  
CITALOPRAM HYDROBROMIDE  
ESCITALOPRAM  
ESCITALOPRAM OXALATE  
FLUOXETINE  
FLUOXETINE HYDROCHLORIDE  
PAROXETINE  
PAROXETINE HYDROCHLORIDE  
SERTRALINE  
SERTRALINE HYDROCHLORIDE  
BUPROPION  
BUPROPION HYDROCHLORIDE  
DESVENLAFAXINE  
DESVENLAFAXINE SUCCINATE

DULOXETINE  
DULOXETINE HYDROCHLORIDE  
VENLAXAFINE  
VENLAFAXINE HYDROCHLORIDE  
MIRTAZAPINE  
TRAZODONE  
TRAZODONE HYDROCHLORIDE  
VORTIOXETINE HYDROBROMIDE  
CALCIUM;CIMICIFUGA RACEMOSA EXTRACT;GENISTEIN;HERBAL EXTRACT  
NOS;MAGNESIUM;PIPER METHYSTICUM RHIZOME

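### Appendix A lifts the hormone ban one week after the last dose, about three weeks before the Week 16 bone-marker sample, while Section 9.8 bars hormones for the whole study

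*Protocol*

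**What the plan says.** **End of the hormone ban.** The header in Protocol Appendix A reads "Prohibited from the time shown until 1 week after the last dose of study medication". Each hormonal row beneath it gives only a start time, counted back from Screening Visit 2. Section 9.8 prohibits hormonal therapies "for the periods stated in exclusion criterion 1, and throughout out the study", and the synopsis identifies Week 16 as the end of study.

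**Restart.** Section 8.6.6 allows restart at Week 12 of prohibited medications that are permitted after treatment ends, and refers to Appendix A for which these are. Section 8.6.7, on the final or early termination visit, says: "Subjects may be re-started on any prohibited medications and menopausal symptom management medications at this time".

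**Non-hormonal treatments.** The row under the same Appendix A header carries its own rule: use "for treatment of menopausal symptoms is not allowed throughout the study".

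**What is measured at Week 16.** Section 10.3.9 states: "Blood for assessment of bone turnover markers will be collected at Baseline, Week 12 and Week 16". Section 8.5 lists the bone markers BALP and P1NP as safety endpoints, as "Change from baseline to Weeks 12 and 16 in" each marker. Section 5.3 gives the reason: NK3 "receptor blockade may result in a reduction in circulating oestrogen concentrations and so safety assessments will, additionally, include an assessment of bone turnover". Hot-flush frequency and severity at Week 16 are secondary endpoints (Section 8.2).

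**SAP handling.** The modified Full Analysis Set (mFAS, SAP 3.1) excludes users of listed non-hormonal and herbal products only, over a period "defined as within 28 days before the start of Screening Visit 2 through to the Week 12 visit, inclusive". SAP 4.8.3 summarises bone markers by visit and treatment without reference to hormone use. SAP 4.8.7 tabulates together all medication used on or after the first randomised dose.

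**The concern.** The two end dates for hormones cannot both hold. The earlier one is the date a site is likely to find, because Section 8.6.6 points to Appendix A at the visit where restart is discussed. The non-hormonal row overrides the header in its own text; the hormonal rows do not.

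Bone turnover is measured because the drug may lower oestrogen. Oestrogen or progestin taken before the Week 16 sample could alter the markers and obscure any change or recovery after treatment. The same hormones treat hot flushes, so the Week 16 diary summaries could be affected too. Nothing planned would separate Week 16 values obtained after a hormone restart from the rest.

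**Working it through.** **Inputs**
- Last dose: the evening before the Week 12 visit (Protocol 9.4).
- Week 12 visit (V12): target Day 85, window Day 81 to 89 (SAP Table 2).
- Week 16 visit (V16): target Day 113, window Day 108 to 118 (SAP Table 2); 4 weeks ± 5 days after the end of treatment (Protocol 8.6.7).
- Diary rule: the last 7 days with data, within 14 days before the visit (SAP 4.3.2).

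**Plan's own figure.** 85 + 28 = 113, which matches the schedule of events.

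**Formulas**
- Last dose = V12 − 1.
- Ban ends = V12 − 1 + 7 = V12 + 6.
- First permitted restart = V12 + 7.
- Longest permitted hormone use before the sample = V16 − (V12 + 7).

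| Case | V12 | First restart day | V16 | Days before sample |
|---|---|---|---|---|
| Nominal | 85 | 92 | 113 | 21 |
| Week 16 early | 85 | 92 | 108 | 16 |
| Week 16 late | 85 | 92 | 118 | 26 |
| Shortest, windows independent | 89 | 96 | 108 | 12 |
| Longest, windows independent | 81 | 88 | 118 | 30 |

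On nominal days the ban ends on Day 91. Counting from that day instead of the first free day adds one day throughout (22 days nominal, range 13 to 31). Under Section 9.8 the figure is 0.

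**Diary days, nominal.** With complete data, the Week 16 summary uses Days 106 to 112. The earliest eligible day is 113 − 14 = 99. Restart on Day 92 precedes these by 106 − 92 = 14 days and 99 − 92 = 7 days, so every eligible diary day falls after the first permitted restart.

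**Diary days, shortest case** (V12 = 89, V16 = 108). The last 7 days begin on Day 101, which is 101 − 96 = 5 days after restart. The earliest eligible day is 108 − 14 = 94, which is 2 days before restart. The statement about every eligible day therefore holds on nominal days but not across all windows.

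**What the analyses would show.** Medication dates are recorded in the eCRF (Protocol 9.7). Table 14.4.7 counts concomitant medications by class and preferred term, by treatment group, without timing. By-subject listings carry the detail. The mFAS reaches neither hormones nor Week 16.

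**The case against.** The strongest reply is that the possible harm is narrow. The half-life is about 15 to 20 hours (Protocol 5.1.3), so one week (168 hours) is roughly 8 to 11 half-lives, and the Week 16 sample is an off-drug recovery sample. Safety data are descriptive, and the oestrogen effect is expected to be modest. Week 16 data are outside the co-primary model (SAP 4.6.1), and Week 16 hot-flush data are only summarised. The documents do not show that any site followed the header, or which way a between-arm bias would run. All of this stands and limits the point to minor. It does not reconcile the two end dates.

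Three stronger readings are tempting, and the documents do not support them.

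- **That Section 8.6.7 independently forbids earlier restart.** Its wording is permissive. It cannot be an exclusive date for all prohibited drugs, because criterion 3 and Appendix A release the interaction drugs earlier. It is consistent with restart at the final visit; the clear conflict is between Appendix A and Section 9.8.
- **That a restart would be visible only in by-subject listings.** Hormones are barred during treatment in every version of the rule. A hormone entry in Table 14.4.7 would therefore point to a deviation or a post-treatment start, by arm. Use before Week 16 also breaches Section 9.8 and could be logged as a deviation. What is missing is timing, and a link to the Week 16 values.
- **That Section 9.8 creates a comparable conflict for interaction drugs.** It ends the ban on narrow-range CYP3A4 substrates, CYP3A4 inhibitors, P-glycoprotein inhibitors and digoxin at the last dose. Criterion 3 and Appendix A say one week later, a 7-day difference. But Section 9.8 allows for exceptions stated elsewhere and itself refers to Appendix A. This is tidying only; CYP3A4 inducers agree at Week 12. That exception clause covers only the interaction list, so it does not resolve the hormone conflict.

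**Conclusion.** The inconsistency is real and minor. Read as written, the Appendix A header permits up to 21 days of hormone use before the Week 16 bone-marker sample on nominal days, and 12 to 30 days across visit windows, where Section 9.8 permits none. These are maximum permitted exposures, not expected ones. They assume that the last dose is taken the evening before the Week 12 visit, that end of treatment is the Week 12 visit, and that hormones start on the first day the header allows. The values at risk are the Week 16 bone markers and the descriptive Week 16 hot-flush summaries. The co-primary analyses at Weeks 4 and 12, the Week 12 bone-marker sample for subjects completing treatment, and the sample size are unaffected.

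**What to change.** **Protocol.** Change the Appendix A header over hormonal and non-hormonal symptom treatments so that the ban runs *until the Week 16 (or Early Termination) visit*. This is one line, with no new data or procedures, and it brings Appendix A into line with Section 9.8. It helps only while subjects are still in treatment or follow-up.

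**SAP.** If follow-up is complete, flag Week 16 bone-marker and diary values obtained after a hormone start. This is one derived variable from medication dates already in the eCRF. It may be the remedy with practical value now: SAP 3.1 and 4.6.2.7 describe the blinded data review as already held.

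**Minor tidying.** In Section 9.8, give the four interaction classes the end date in criterion 3 and Appendix A, *until 1 week after the last dose of IMP*, and leave inducers at Week 12. This is one sentence.

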**METHODS**

First, in order to arrive at some example TRUE underlying dose-response scenarios, prior data on hot flush reduction was examined. NT-814 has shown efficacy in reduction of hot flushes over a 2-week period in a Phase 1/2a trial. Mean reductions in hot flush frequency of up to 9 per day from a baseline frequency ~10-12 were observed (with an observed SD of change from baseline ranged between ~3.4 to ~4.9; SD back-calculated from SE's from the analysis model yielded SD's of change ~3.7). In order to obtain longer term prior data to inform on expected variability, the Duavee label was also examined. It yielded SD's of change ~4.4 after 4 weeks' treatment and ~3.6 after 12 weeks' treatment. Based on these prior data, an SD=4.4 and somewhat conservative magnitudes of treatment effect were used to simulate adaptive design outcomes and performance characteristics. The following TRUE underlying dose-response curves were examined:

label	Assumed TRUE underlying mean hot flush frequency reduction from baseline (SD=4)				
	placebo (dose0)	dose1	dose2	dose3	dose4
DRCID 1	4	4	5	6	7
DRCID 2	4	5	6	7	8
DRCID 3	4	5	6	8	8
DRCID 4	4	6	8	8	8

The total sample size for the trial yields high power for the expected large difference from placebo in hot flush reduction from baseline and adequate power for moderate difference.

Assuming a common standard deviation (SD) of 4.4, N=27 per treatment group has ~95% power ( $\alpha=0.05$  2-sided) via trend test across all doses including placebo if the true underlying dose response is non-decreasing from a reduction of 4 hot flushes on placebo up to 8 on the highest dose of NT-814. N=33 per treatment group is required for 95% power for pairwise comparison of the highest dose to placebo under these same assumptions. Hence, a total of 150 completed subjects (30 x 5) was used for the simulations of adaptive design. [Note, the actual performance / power for the adaptive designs may be higher than the values cited in this report since additional subjects will be added to selected dose groups to better inform on safety.] The actual sample size will be determined by the adaptive dose-finding design algorithm.

The sample size allows for 95% power since each of the four co-primary endpoints are required to demonstrate statistical significance in order to yield a firm conclusion of beneficial treatment effect on hot flushes. Conservatively, assuming independence among the four endpoints, this would yield approximately 81% power overall for achieving statistical significance for each of the four endpoints. Thus, overall power for the trial is estimated to be at least 81%; the actual power depends on the unknown magnitudes of correlations among the co-primary endpoints.

Adaptive dose-finding design algorithms use results from interim analysis (IA) of accumulating data from the trial to modify dose-choices and / or randomization ratios for subsequent subjects entering the trial. Three numbers of IA and two adaptive dose-finding algorithms were evaluated for each of the four potential TRUE underlying dose-response curves (total 24 scenarios = 4 DR curves X 3 cohort sizes X 2 design algorithms). The three IA sizes evaluated are (i) no IA's (i.e., N=15 per dose group to compare to a non-adaptive design), (ii) two IAs, and (iii) five IAs. Both the 2-IA and 5-IA designs randomize the initial 25 patients 1:1:1:1:1 to the 5 dose groups (note, placebo is the zero dose group) to obtain a reasonable amount of seeding data upon which to begin the adaptation. Note, the actual planned size of the first cohort is N=30, which would yield results between those of the two sample size scenarios simulated for the adaptive designs. Hence, the actual performance characteristics of the trial fall between the those two sample size scenarios. Since the timing of the actual IA's may vary due to logistical / enrolment constraints, these two scenarios are representative of the those expected during the trial. Then the 2-IA design carries out a second IA after N=50 total patients are observed, and then the final analysis is

---

carried out after the 75 patients are completed. After the initial IA at N=25, the 5-IA design carries out an IA after results of each 10 patients are added to the accumulating data.

The two adaptive algorithms are (i) a Bayesian adaptive Emax (S-shaped) dose-response model fit at each IA (COMPASS User Manual), and (ii) a model based on classical T-statistics at each IA (Ivanova, 2008). The Emax design uses a "vague" Bayesian prior distribution on each of the four parameters of the S-shaped Emax model in combination with the observed data to estimate the posterior distribution of the Emax model parameters from which estimates of mean response at each dose are obtained, along with their SE's. Then randomization ratios are chosen for the next cohort to minimize the variances of the resulting Emax model estimates at two target levels of response, namely hot flush reductions of 6 per day and of 8 per day. The Emax algorithm was set up to recommend stopping randomization to a given dose if (a) the probability is > 90% that the mean hot flush reduction is at least 8 at that dose, or (b) the probability is <20% that the mean hot flush reduction is at least 5 (i.e., >80% probability that the mean hot flush reduction is <5).

The T-statistic design relies on isotonic regression (i.e., best-fit non-decreasing dose-response curve) derived estimated means for each dose and then computes the resultant T-statistic for estimated mean difference from each target level of response (hot flush reduction of 6 and of 8) for each dose. Then the subjects in the next cohort are split among the two doses with T-statistics pointing closest to each target level of response and placebo. The sample sizes of each cohort are always 10 on placebo for the 2 IA design, and always 5 on placebo for the 5 IA design, to yield N=30 on placebo for the final analysis. For the simulations, the subjects assigned to the active doses are randomized according to the randomization ratio indicated by the adaptive design algorithm for each cohort after the first. The only stopping criteria recommendation available for the T-statistic in the simulation software (Cytel's COMPASS V1.1) is futility stopping; hence, if probability of a significant difference from placebo is <5% for a given dose based on the IA results, then the algorithm recommends that dose is dropped from any further randomization to it.

The 24 scenarios (4 DR curves X 3 cohort sizes X 2 design algorithms) were each simulated 500 times, and the following performance characteristics, averaged across the 500 simulations, were summarized in Tables 1a and 1b

- Average total sample size
- Power to reject a flat dose-response curve ( $\alpha=0.05$  2-sided), and conclude statistically significant NT-814 effect
- Average sample size assigned to each dose
- Average estimated dose level (among doses 1,2,3,4) closest to the target hot flush reduction from baseline of 6
- Percent of simulations choosing the correct dose with TRUE underlying hot flush reduction from baseline of 6
- Percent of simulations choosing the correct dose or adjacent to the correct dose with TRUE underlying hot flush reduction from baseline of 6
- Average estimated dose level (among doses 1,2,3,4) closest to the target hot flush reduction from baseline of 8
- Percent of simulations choosing the correct dose with TRUE underlying hot flush reduction from baseline of 8
- Percent of simulations choosing the correct dose or adjacent to the correct dose with TRUE underlying hot flush reduction from baseline of 8

In order to account for recruitment rate and lag of data collection and analysis as patients continually enter the trial, the simulations were run assuming a 6-week lag for each patient entering and their 4 week hot flash frequency data entering the interim analysis. An average recruitment rate of 5 patients per week was assumed, since the software cannot accommodate varying recruitment.

It should be noted that the analysis models for the actual trial data will be longitudinal mixed effects models to model the correlation structure of all hot flash frequency data at each week from baseline to week 12. Due to software limitations, the simulations only assume available data of Week 4, so the performance characteristics in this report are likely conservative.

